#### 4.2.2. Secondary efficacy endpoints

- Area Under the Curve (AUC) for the serum C-peptide level during the first 4 hours of an MMTT, normalized by the number of Islet Equivalent (IEQ)/kg [Time frame: day 75±14 and 365±14 after the transplant].

- Average daily insulin requirements [time frame: day 75±14 and 365±14 after the transplant].  
For the purpose of this protocol, daily insulin is reported as IU/kg and intake averaged over the previous week.

- Basal (2 basal samples in the range between -20 to 0) to 240 min time course of glucose, C-peptide and insulin derived from the MMTT [time frame: day 75±14 and 365±14 after the transplant].

- $\beta$ -cell function as assessed by  $\beta$ -score [time frame: day 75±14 and 365±14 after the transplant].

- The proportion of patients with an HbA1c  $\leq 6.5\%$  [time frame: day 365±14 after the transplant].

- Cumulative number of severe hypoglycemic events [time frame: from day 75±14 to day 365±14 after the transplant].

For the purpose of this protocol, a severe hypoglycemic event is defined as an event with one of the following symptoms: "memory loss, confusion, uncontrollable behavior, irrational behavior, unusual difficulty in awakening, suspected seizure, seizure, loss of consciousness, or visual symptoms", in which the subject was unable to treat him/herself and which was associated with either a blood glucose level  $<54$  mg/dL or prompt recovery after oral carbohydrate, i.v. glucose, or glucagon administration.

- The proportion of patients with an HbA1c  $\leq 6.5\%$  at day 365±14 AND are free of severe hypoglycemic events from day 75±14 to day 365±14 inclusive [time frame: day 365±14 and from day 75±14 to day 365±14 after the transplant].

#### 4.2.3. Safety endpoints

- Incidence and severity of Adverse Events and Serious Adverse Events [time frame: throughout the study up to day 365±14 after the transplant].

- Standard laboratory tests including hematology (hematocrit, hemoglobin, red blood cells, platelets, white blood cells, differential white blood cells count), clinical chemistry (sodium, potassium, serum creatinine, blood urea nitrogen, total bilirubin, alanine aminotransferase (ALT), aspartate aminotransferase (AST) and coagulation (International Normalized Ratio (INR), partial thromboplastin time (PTT)) [time frame: pre-transplant hospital admission and post-transplant hospital discharge].
- Vital signs, i.e. blood pressure (BP) and heart rate (HR) [time frame: pre-transplant hospital admission and post-transplant hospital discharge].
- ALT/AST, INR/PTT, fibrin degradation products (XDPs), C-reactive protein (CRP) [time frame: all daily from day 1 up to day 7 after the transplant; ALT/AST also on day 75±5 after the transplant].
- Weight loss from pre-transplant value [time frame: day 75±14 and 365±14 after the transplant].
- Serum level of albumin and pre-albumin (absolute and change from pre-transplant value) [time frame: day 75±14 and 365±14 after the transplant].
- Proportion of patients falling into one of the following levels of steatorrhea severity [time frame: day 75±14 and 365±14 after the transplant].  
For the purpose of this protocol, levels of steatorrhea severity (evaluated in the 4 weeks prior to day 75±14 and 365±14), are defined as:
  - No steatorrhea;
  - Steatorrhea few times per week;
  - Steatorrhea daily;
  - Stool incontinence.
- Proportion of patients falling into one of the following malnutrition risk levels (poor prognosis, significant risk, increased risk, normal) according to pre-albumin level [time frame: day 75±14 and 365±14 after the transplant].  
For the purpose of this protocol, malnutrition risk levels are defined as [adapted from *Bernstein, 1995*]:
  - Poor prognosis = pre-albumin level <5.0 mg/dL
  - Significant risk = pre-albumin level 5.0 to 10.9 mg/dL
  - Increased risk = pre-albumin level 11.0 to 15.0 mg/dL
  - Normal = pre-albumin level > 15.0 (up to 35.0) mg/dL
- Cumulative number of episodes of documented hypoglycemia (documented symptomatic; asymptomatic) [time frame: from day 75±14 to day 365±14 after the transplant].  
For the purpose of this protocol, the following definition applies [*Diabetes Care, 2005*]:
  - Documented symptomatic hypoglycemia = An event during which typical symptoms of hypoglycemia are accompanied by a measured plasma glucose concentration ≤70mg/dL.
  - Asymptomatic hypoglycemia = An event not accompanied by typical symptoms of hypoglycemia, but with a measured plasma glucose concentration ≤70mg/dL.
- Cumulative number of diabetic ketoacidosis-related events [time frame: from day 75±14 to day 365±14 after the transplant].  
For the purpose of this protocol, a diabetic ketoacidosis event is defined as the presence of [*Pediatrics, 2004*]:
  - hyperglycemia (blood glucose >200 mg/dL);
  - pH <7.3 or HCO3 <15;
  - ketones positive in the serum or urine.

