During hospital stay, all AEs (see details in Sections 8.2.) and CMEDs (see details in Sections 6.5.) will be recorded.

For all measurements above, the actual date and time of assessment, including date of sampling, will be recorded in the CRF.

Apart from compliance with protocol procedures up to day 7 post-transplant, hospital discharge will be primarily based on criteria related to total pancreatectomy (the major surgical procedure in total pancreatectomy followed by IAT) and will comply with each site's hospital standards. However, at all sites, at least the following criteria will be complied with: "A patient will be discharged if he/she at least is ambulating, has adequate nutrition (oral, enteral, or Total Parenteral Nutrition (TPN), is not requiring any intravenous medications which require inpatient monitoring, pain is adequately treated, and he/she has a stable plan for glycemic control (management of blood glucose testing and insulin administration at home)".

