### 8.3. RECORDING

AE data should be obtained through observation of the patient, from any information volunteered by the patient, or through patient questioning. Specifically, patients will be asked about any episode of documented hypoglycemia and ketoacidosis-related events occurring from the transplant day up to day  $75 \pm 14$  post-transplant. Any episodes will be reported as an AE or SAE, as appropriate. In addition, the Investigator will capture and report episodes of non-documented hypoglycemia throughout study participation.

All AEs (serious and non-serious) encountered during the clinical study will be recorded in the appropriate section of the CRF as per the recording period defined in paragraph 8.3.1. It is important that this includes the duration of the AE (onset/resolution dates), the relationship to the drug, the severity, the outcome and relevant concomitant treatments dispensed (or other action taken) (see Sections 8.3.2. and 8.3.3. below).

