### 8.3.1. AE recording period

All AEs (serious and non-serious) which occur during each hospital stay will be recorded in the CRF. In addition, SAEs and relevant untoward events that occur subsequent to each hospital discharge will be recorded in the CRF.

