## 14.4. APPENDIX 4 - STUDY FLOW CHART

Test/Examination	HOSPITAL STAY											FOLLOW-UP	
	Screening	day -1	day 0 Tx day	day 1	day 2	day 3	day 4	day 5	day 6	day 7	Hospital discharge	day 75±14 post transplant	day 365±14 post transplant
Informed consent	X												
Inclusion/exclusion criteria	X												
BP, HR, weight, height 	X										X 	X 	X 
Safety laboratory tests	X										X		
Pregnancy test	X												
Renal reserve/function  & Total bilirubin	X		X	X	X	X	X	X					
Albumin and pre-albumin	X											X	X
Concurrent sepsis	X												
Pre-operative portal hypertension	X												
miR-375; Inflammatory chemokines/cytokines 	XX 	XXX 	X 		X 		X 		X 				
Study drug administration 		X-----								X-----			
PK sampling 			X		X		X		X		X 		
ALT/AST			X	X	X	X	X	X	X	X		X	
XDP, INR/PTT, CRP			X	X	X	X	X	X	X	X			
Average daily insulin; HbA1c												X	X
Severe, Documented Symptomatic, Asymptomatic hyperglycemia events												X-----	X
MMTT  ; Glucose, C-peptide, insulin												X	X
β-score – TEF calculation												X	X
Steatorrhea  and malnutrition risk 												X	X
Adverse Events		X-----									Record all AEs up to each hospital discharge Then, only SAEs -----X		
Concomitant Medication	X-----	Record all CMEDs up to each hospital discharge Then, only drugs used for SAEs, oral hypoglycemic drugs and forbidden medications -----X											

1 = Measure only BP and HR at hospital discharge. Measure only weight at follow-up visits.

2 = Assess Creatinine clearance on pre-transplant. Assess creatinine clearance AND urine output from day 1 to day 6 post-transplant.

3 = Store a serum sample for centralized assay as detailed in **Appendix 14.6.3**. Take the 2 chemokines/cytokines pre-transplant samples 6 to 24 hours apart; obtain all basal samples before surgery and before the Investigational Product administration is started. Take post-transplant samples @ 6, 12, 24, 72, 120 and 168hrs after islet infusion.

4 = Start study drug infusion approximately 12 (6-18) hours before islet infusion. Obtain PK ideally in the morning (day 1, 3, 5 post-transplant). Obtain (if you are one of the 2 selected sites) a sample just prior to, and then 1, 3, 5, 6, 8, and 12 hours after the end of study drug administration.

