### 4.2.2 Safety Variables

- Incidence and severity of adverse events (AEs) and serious adverse events (SAEs) throughout the study up to Day 365  $\pm$  14 days after IAT.
- Standard laboratory tests including hematology (hematocrit, hemoglobin, red blood cells, platelets, white blood cells, differential white blood cells count), clinical chemistry (sodium, potassium, serum creatinine, blood urea nitrogen, total bilirubin, ALT, AST), and coagulation

REP0112

Statistical Analysis Plan

(international normalized ratio [INR], partial thromboplastin time [PTT]) at pre-transplant hospital admission and post-transplant hospital discharge.

- Vital signs, i.e. systolic and diastolic blood pressure (BP) and heart rate (HR) at pre-transplant hospital admission and post-transplant hospital discharge.
- ALT, AST, INR, PTT, fibrin degradation products (XDPs), and C-reactive protein (CRP), all daily from Day 1 up to Day 7 after IAT; ALT and AST also on Day 75 ± 5 days after IAT.
- Weight loss from pre-transplant value at Day 75 ± 14 days and Day 365 ± 14 days after IAT.
- Serum level of albumin and pre-albumin, absolute and change from pre-transplant value, at Day 75 ± 14 days and Day 365 ± 14 days after IAT.
- Proportion of patients falling into one of the following levels of steatorrhea severity at Day 75 ± 14 days and Day 365 ± 14 days after IAT.

For the purpose of this protocol, levels of steatorrhea severity (evaluated in the 4 weeks prior to Day 75 ± 14 days and Day 365 ± 14 days), are defined as:

- No steatorrhea;
- Steatorrhea few times per week;
- Steatorrhea daily;
- Stool incontinence.

- Proportion of patients falling into one of the following malnutrition risk levels according to pre-albumin level at Day 75 ± 14 days and Day 365 ± 14 days after IAT.

For the purpose of this protocol, malnutrition risk levels are defined as (adapted from Bernstein, 1995):

- Poor prognosis = pre-albumin level <5.0 mg/dL
- Significant risk = pre-albumin level 5.0 to 10.9 mg/dL
- Increased risk = pre-albumin level 11.0 to 15.0 mg/dL
- Normal = pre-albumin level > 15.0 (up to 35.0) mg/dL

- Cumulative number of episodes of documented hypoglycemia (documented symptomatic; asymptomatic) from Day 75 ± 14 days to Day 365 ± 14 days after IAT.

For the purpose of this protocol, the following definition applies (Diabetes Care, 2005):

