### 7.6.1 Adverse Events

All reported verbatim adverse event terms will be mapped to standard system organ classes and preferred terms using the MedDRA Dictionary as specified in the Data Management Plan for this protocol.

REP0112

Statistical Analysis Plan

A treatment emergent adverse event (TEAE) is defined as any recorded adverse event which started on or after Day 1 of investigational product administration. If the start date of an adverse event is incomplete or missing, the event will be assumed to be a TEAE, unless the incomplete start date (month and/or year) or the stop date (complete or incomplete) clearly indicates that the event started prior to dosing.

The relationship of each adverse event to investigational product will be recorded as none, unlikely, possible, probable, or highly probable. If a relation is missing for an adverse event, the relation of the event to investigational product will conservatively be assumed to be highly probable for summarization.

The severity of each adverse event will be classified as mild, moderate, or severe. If the severity of an adverse event is missing, the severity of the event will conservatively be assumed to be severe for summarization.

Serious adverse events will be those events indicated as such on the CRF (a "Yes" response to "Serious").

An overview of TEAEs will summarize the number and percentage of patients and the number of events in the following categories: any TEAE, any TEAE by relationship to investigational product, any TEAE by severity, any serious TEAE, any serious TEAE by relationship to investigational product, any serious TEAE by severity, any TEAE resulting in early withdrawal from study, and death. For this overview, patients and events will be counted at each level of relationship to investigational product or severity at which an event is experienced (and not by worst relationship to investigational product and maximum severity).

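### The AE endpoint runs to day 365, but general non-serious AEs are recorded only in hospital, the post-discharge rules conflict, and the SAP pools both periods in one set of tables

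*Protocol*

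**What the plan says.** Protocol 4.2.3 lists, as the first safety endpoint, "Incidence and severity of Adverse Events and Serious Adverse Events [time frame: throughout the study up to day 365±14 after the transplant". The synopsis (Protocol 1) has the same line, and SAP 4.2.2 carries it over: "Incidence and severity of adverse events (AEs) and serious adverse events (SAEs) throughout the study up to Day 365".

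The collection rules are spread over several places:

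- Protocol 8.3.1, in hospital: "All AEs (serious and non-serious) which occur during each hospital stay will be recorded in the CRF". After discharge: "SAEs and relevant untoward events that occur subsequent to each hospital discharge will be recorded in the CRF". The second category in that sentence is not defined.
- The flow chart in Protocol Appendix 14.4: "Record all AEs up to each hospital discharge Then, only SAEs".
- Protocol 7.2 names only SAEs as the events to be recorded at the day 75 and day 365 visits.
- Protocol 8.3 requires patients to be asked about documented hypoglycemia and ketoacidosis-related events from the transplant day to day 75±14, and says "Any episodes will be reported as an AE or SAE, as appropriate". It also has the investigator report non-documented hypoglycemia for as long as the patient is in the study.

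The date of discharge is not fixed. Protocol 7.1.5 ties it mainly to recovery from the pancreatectomy and says it "will comply with each site's hospital standards". The same paragraph sets minimum criteria for every site and expects protocol procedures up to day 7.

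SAP 7.6.1 defines a treatment-emergent AE as "any recorded adverse event which started on or after Day 1 of investigational product administration". The planned tables give patients and events by system organ class and preferred term, then by relationship and by severity.

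**The concern.** The endpoint promises a year of AE incidence and severity. For non-serious events in general, the protocol collects only the hospital stay, which ends on a date that varies by patient and site. What is collected afterwards depends on which section a site follows. The SAP then puts everything recorded into the same tables.

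Three things follow from the text alone. The percentage of patients with a given AE is not a 365-day incidence, although the endpoint calls it one. The relationship and severity tables combine a period in which nearly every event counts with a much longer one in which events enter mainly because they are serious or of a named type. Sites may also differ in which non-serious events they record after discharge.

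SAP 8 has the independent statistician use the SAP as the guide for the monitoring committee's outputs, so the committee may be shown the same mixture.

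**Working it through.** The documents state no figure on this point, so the check is mainly a comparison of texts.

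**Step 1. Endpoint against collection rules.**

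| Source | In hospital | After discharge |
|---|---|---|
| Protocol 1 and 4.2.3; SAP 4.2.2 (endpoint) | AEs and SAEs | AEs and SAEs, to day 365±14 |
| Protocol 8.3.1 | All AEs | SAEs and one undefined category |
| Protocol Appendix 14.4 | All AEs | SAEs only |
| Protocol 7.2 | not addressed | SAEs, at the two visits |
| Protocol 8.3 | refers to 8.3.1 | Documented hypoglycemia and ketoacidosis to day 75±14; non-documented hypoglycemia throughout |
| SAP 7.6.1 (analysis) | Any recorded event | Any recorded event; no end date, no split |

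All AEs in the second column is itself subject to the short list of exempt events in Protocol 8.5.

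**Step 2. Two test cases.** Take a mild, non-serious skin reaction at home on day 100. The endpoint counts it. The flow chart and 7.2 do not collect it. Under 8.3.1 it is collected only if someone judges that it fits the undefined category. Now take a non-serious documented hypoglycemic episode at home on day 40. Protocol 8.3 requires it as an AE; the flow chart does not. So the rules disagree with the endpoint and with each other.

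**Step 3. Does the SAP repair it?** No. The definition in 7.6.1 has a start and no end. The tables in 7.6.1 and section 10 have no split at discharge and no adjustment for time under observation. Section 10 lists no table of length of stay. By contrast, Protocol 4.2.3 gives routine laboratory tests and vital signs an explicit admission-to-discharge window, so the authors limited the window where they meant to.

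**Step 4. How much of the year has full capture?** The formula is discharge day / 365. No length of stay is given, so the discharge day is an assumption, starting at day 7 because protocol procedures run to that day:

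- day 7: 7/365 = 1.9%
- day 14: 14/365 = 3.8%
- day 21: 21/365 = 5.8%
- day 28: 28/365 = 7.7%

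For discharge on day 7, the ±14-day visit window gives 7/379 = 1.8% to 7/351 = 2.0%. These figures cover the first stay only. Section 8.3.1 and the flow chart refer to each hospital stay or discharge, so full recording may resume on readmission, which would raise the coverage and make it less uniform.

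**Step 5. Can the events be separated afterwards?** Yes. Protocol 8.3 records onset dates, and SAP section 10 plans listings of adverse events and of hospital discharge. SAP 1.1 has the plan finalized before database lock.

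**The case against.** The strongest reply has four parts.

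First, the window is disclosed. Protocol 8.3 says AEs are recorded for the period set in 8.3.1, and limiting non-serious collection after a 7-day infusion of a drug with a human half-life of 1.0 to 1.5 hours (Protocol 2.3) is a defensible choice. That stands as a defense of the collection rule. It does not defend an endpoint that claims more than the rule collects, or 8.3.1 and the flow chart giving different rules.

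Second, follow-up is not serious-only. Section 8.3.1 has its extra category, 8.3 keeps non-documented hypoglycemia open for the whole study, and documented hypoglycemia and ketoacidosis from day 75 to day 365 have their own endpoints and analyses (SAP 7.6.6 and 7.6.7). This is right, and it is why later capture is called selective here.

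Third, a reader might infer that the arm with the longer stay will show more AEs merely because it is watched longer. The documents do not support that as a finding. Nothing in them shows that reparixin changes length of stay. The trial is double-blind and blocked within centre (Protocol 9.2), so site discharge practice should roughly balance. An event that prolongs hospitalization is an SAE by definition (Protocol 8.1.2) and is captured in any case. The AE tables are descriptive. Discharge does occur after randomization, and one criterion is a stable plan for glycemic control, so an effect on stay is possible. Any numerical size for it would rest wholly on assumed stays and event rates.

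Fourth, cutting the comparison at a fixed early day would discard fully recorded in-hospital events. This also stands: a fixed window can supplement the in-hospital table but should not replace it.

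**Conclusion.** The endpoint and the planned tables do not match as written. Carried out to the letter, the plan yields TEAE, severity and relationship tables that mix full in-hospital capture with selective and inconsistently specified post-discharge capture, and these do not estimate AE incidence or severity to day 365. This conclusion rests on the text alone and needs no difference between arms.

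The size can only be illustrated: 1.9% to 7.7% of 365 days under full capture, if first discharge falls between day 7 and day 28 and readmissions are left aside.

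Two stronger readings go beyond the documents. Bias between arms would arise only if treatment affects length of stay, which is not shown. A shift of the severity table toward severe events is plausible, because later events enter largely on seriousness, but Protocol 8.3.3 grades severity separately from seriousness and no size can be given.

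**What to change.** 1. In Protocol 1 and 4.2.3 and in SAP 4.2.2, restate the endpoint as (a) all AEs, serious and non-serious, from the start of Investigational Product to initial hospital discharge, and (b) SAEs from the start of Investigational Product to day 365±14, plus the named post-discharge events.
2. In SAP 7.6.1, present the TEAE, severity and relationship tables separately for the in-hospital and post-discharge periods. Keep all in-hospital AEs, and summarize length of stay by arm.
3. Add a supplementary table from the start of Investigational Product to day 7 post-transplant, when nearly all patients should still be under full recording. It covers the nominal infusion: 168 − 12 = 156 hours, or 6.5 days, after islet infusion. For the roughly 5 patients expected not to receive IAT (Protocol 9.1), use an equivalent cut from infusion start, nominally 7 × 24 + 12 = 180 hours.
4. Reconcile Protocol 8.3.1, 8.3, 7.2 and Appendix 14.4 on which non-serious events are recorded after discharge. Define the open category in 8.3.1, include non-documented hypoglycemia throughout the study, and say whether full recording resumes on readmission.

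The cost is a few more tables and a narrower headline claim for non-serious AEs. Items 1 to 3 use dates already collected and can be done before database lock. Item 4 cannot be applied evenly to the past: the amendment reports 86 patients already transplanted. The study report should therefore say that earlier post-discharge recording followed conflicting rules.

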#### 4.2.4. Exploratory endpoints

- Time course of inflammatory chemokines/cytokines as assessed by serum level of CXCL8, CCL2 (MCP-1), CCL3, CCL4, CXCL10 (IP-10), CXCL9 (MIG), IL-6, IL-10, INF-γ, TNF-α, and IL-1β [time frame: pre-infusion hospital admission (2 basal samples collected 6 to 24 hrs apart;

both samples will be obtained before surgery and before Investigational Product administration is started) and 6, 12, 24, 72, 120 and 168hrs after the end of islet infusion].

- Proportion of patients who are randomized but do not receive IAT [time frame: transplant day].
- Time course of serum microRNA-375 (miR-375) [time frame: pre-infusion hospital admission (sample will be obtained before surgery and before Investigational Product administration is started) and 6, 12, 24, 72, 120 and 168hrs after the end of islet infusion].

